## 8. INFORMED CONSENT, TRIAL RECORDS, DATA PROTECTION, PUBLICATION POLICY, AND ADMINISTRATIVE STRUCTURE

The trial will be carried out in compliance with the protocol, the ethical principles laid down in the Declaration of Helsinki, in accordance with the ICH Harmonized Guideline for Good Clinical Practice (GCP), relevant BI Standard Operating Procedures (SOPs), and other relevant regulations. Investigators and site staff must adhere to these principles. Deviation from the protocol, the principles of ICH GCP or applicable regulations as will be treated as “protocol deviation”.

Standard medical care (prophylactic, diagnostic and therapeutic procedures) remains the responsibility of the treating physician of the patient.

The investigator will inform the sponsor immediately of any urgent safety measures taken to protect the trial patients against any immediate hazard, as well as of any serious breaches of the protocol or of ICH GCP.

The Boehringer Ingelheim transparency and publication policy can be found on the following web page: [trials.boehringer-ingelheim.com](http://trials.boehringer-ingelheim.com). The rights of the investigator and of the sponsor with regard to publication of the results of this trial are described in the investigator contract. As a rule, no trial results should be published prior to finalisation of the Clinical Trial Report.

The certificate of insurance cover is made available to the investigator and is stored in the ISF.

### 8.1 TRIAL APPROVAL, PATIENT INFORMATION, INFORMED CONSENT

This trial will be initiated only after all required legal documentation has been reviewed and approved by the respective Institutional Review Board (IRB / Independent Ethics Committee (IEC and competent authority (CA) according to national and international regulations. The same applies for the implementation of changes introduced by amendments.

Prior to patient participation in the trial, written informed consent must be obtained from each patient (or the patient's legally accepted representative) according to ICH-GCP and to the regulatory and legal requirements of the participating country. Each signature must be personally dated by each signatory and the informed consent and any additional patient-information form retained by the investigator as part of the trial records. A signed copy of the informed consent and any additional patient information must be given to each patient or the patient's legally accepted representative.”

The patient must be given sufficient time to consider participation in the trial. The investigator or delegate obtains written consent of the patient's own free will with the informed consent form after confirming that the patient understands the contents. The investigator or [ ] delegate must sign (or place a seal on) and date the informed consent form. If a trial collaborator has given a supplementary explanation, the trial collaborator also signs (or places a seal on) and dates the informed consent.

Re-consenting may become necessary when new relevant information becomes available and should be conducted according to the sponsor's instructions.

Proprietary confidential information © 2021 Boehringer Ingelheim International GmbH or one or more of its affiliated companies

If study conduct may need to be adjusted (see [Sections 6.1](#) and [10.2](#)) during the COVID-19 pandemic, the patient must be made aware of any modifications and agreement needs to be obtained prior to them being implemented.

The consent and re-consenting process should be properly documented in the source documentation.

## **8.2 DATA QUALITY ASSURANCE**

A risk-based approach is used for trial quality management. It is initiated by the assessment of critical data and processes for trial subject protection and reliability of the results as well as identification and assessment of associated risks. An Integrated Quality and Risk Management Plan documents the rationale and strategies for risk management during trial conduct including monitoring approaches, vendor management and other processes focusing on areas of greatest risk.

Continuous risk review and assessment may lead to adjustments in trial conduct, trial design or monitoring approaches.

A quality assurance audit/inspection of this trial may be conducted by the sponsor, sponsor's designees, or by IRB / IEC or by regulatory authorities. The quality assurance auditor will have access to all medical records, the investigator's trial-related files and correspondence, and the informed consent documentation of this clinical trial.

## **8.3 RECORDS**

CRFs for individual patients will be provided by the sponsor. See [Section 4.1.5.2](#) for rules about emergency code breaks. For drug accountability, refer to [Section 4.1.8](#).

### **8.3.1 Source documents**

In accordance with regulatory requirements, the investigator should prepare and maintain adequate and accurate source documents and trial records that include all observations and other data pertinent to the investigation on each trial patient. Source data as well as reported data should follow the "ALCOA principles" and be attributable, legible, contemporaneous, original and accurate. Changes to the data should be traceable (audit trail).

Data reported on the CRF must be consistent with the source data or the discrepancies must be explained.

The current medical history of the patient may not be sufficient to confirm eligibility for the trial and the investigator may need to request previous medical histories and evidence of any diagnostic tests. In this case, the investigator must make at least one documented attempt to retrieve previous medical records. If this fails, a verbal history from the patient, documented in their medical records, would be acceptable.

Copies of source documents necessary for adjudication will be provided to CRO responsible for adjudication . Before sending or uploading those copies, the investigator must ensure that all patient identifiers (e.g. patient's name, initials, address, phone number, social security number) have properly been removed or redacted from any copy of the patients' source documents.

If the patient is not compliant with the protocol, any corrective action e.g. re-training must be documented in the patient file.

For the CRF, data must be derived from source documents, for example:

Proprietary confidential information © 2021 Boehringer Ingelheim International GmbH or one or more of its affiliated companies

- Patient identification: gender, year of birth (in accordance with local laws and regulations)
- Patient participation in the trial (substance, trial number, patient number, date patient was informed)
- Dates of patient's visits, including dispensing of trial medication
- Medical history (including trial indication and concomitant diseases, if applicable)
- Medication history
- Adverse events and outcome events (onset date (mandatory), and end date (if available))
- Serious adverse events (onset date (mandatory), and end date (if available))
- Concomitant therapy (start date, changes)
- Originals or copies of laboratory results and other imaging or testing results, with proper documented medical evaluation (in validated electronic format, if available)
- Completion of patient's participation in the trial (end date; in case of premature discontinuation document the reason for it).
- Prior to allocation of a patient to a treatment into a clinical trial, there must be documented evidence in the source data (e.g. medical records) that the trial participant meets all inclusion criteria and does not meet any exclusion criteria. The absence of records (either medical records, verbal documented feedback of the patient or testing conducted specific for a protocol) to support inclusion/exclusion criteria does not make the patient eligible for the clinical trial.

### 8.3.2 Direct access to source data and documents

The investigator /institution will allow site trial-related monitoring, audits, IRB / IEC review and regulatory inspections. Direct access must be provided to the CRF and all source documents/data, including progress notes, copies of laboratory and medical test results, which must be available at all times for review by the CRA, auditor and regulatory inspector (e.g. FDA). They may review all CRFs and informed consents. The accuracy of the data will be verified by direct comparison with the source documents described in [Section 8.3.1](#). The sponsor will also monitor compliance with the protocol and GCP.

In the event of force majeure or other disrupting circumstances (e.g. pandemic, see [Section 6.1](#)), site access may be restricted thus limiting the ability to perform standard site monitoring activities such as on-site source data review and source data verification. Therefore, some of these activities may be performed remotely or replaced by centralized monitoring to the extent possible, based on a documented risk assessment and in alignment with local regulations.

### 8.3.3 Storage period of records

#### Trial sites:

The trial sites must retain the source and essential documents (including ISF) according to contract or the local requirements valid at the time of the end of the trial (whatever is longer).

#### Sponsor:

The sponsor must retain the essential documents according to the sponsor's SOPs.

## 8.4 EXPEDITED REPORTING OF ADVERSE EVENTS

BI is responsible to fulfil their legal and regulatory reporting obligation in accordance with regulatory requirements.

## 8.5 STATEMENT OF CONFIDENTIALITY AND PATIENT PRIVACY

Data protection and data security measures are implemented for the collection, storage and processing of patient data in accordance with the principles 7 and 12 of the WHO GCP handbook.

Individual patient data obtained as a result of this trial is considered confidential and disclosure to third parties is prohibited with the following exceptions:

Personalised treatment data may be given to the patient's personal physician or to other appropriate medical personnel responsible for the patient's welfare. Data generated at the site as a result of the trial need to be available for inspection on request by the participating physicians, the sponsor's representatives, by the IRB / IEC and the regulatory authorities.

### 8.5.1 Collection, storage and future use of biological samples and corresponding data

Not applicable.

## 8.6 TRIAL MILESTONES

The **start of the trial** is defined as the date when the first patient in the whole trial signs informed consent.

The **end of the trial** is defined as the date of the last visit of the last patient in the whole trial ("Last Patient Completed"). The "**Last Patient Last Treatment**" (LPLT) date is defined as the date on which the last patient in the whole trial is administered the last dose of trial treatment (as scheduled per protocol or prematurely). Individual investigators will be notified of SUSARs occurring with the trial medication until 30 days after LPLT at their site. **Early termination of the trial** is defined as the premature termination of the trial due to any reason before the end of the trial as specified in this protocol.

**Temporary halt of the trial** is defined as any unplanned interruption of the trial by the sponsor with the intention to resume it.

**Suspension of the trial** is defined as an interruption of the trial based on a Health Authority request.

## 8.7 ADMINISTRATIVE STRUCTURE OF THE TRIAL

The trial is sponsored by Boehringer Ingelheim (BI).

A Coordinating Investigator is responsible to coordinate investigators at the different sites participating in this trial. Tasks and responsibilities are defined in a contract.

Relevant documentation on the participating (Principal) Investigators (e.g. their curricula vitae) will be filed in the ISF. The investigators will have access to the BI clinical trial portal (Clinergize) to facilitate document exchange and maintain electronic ISF.

BI has appointed a Clinical Trial Leader (CT Leader), responsible for coordinating all required activities, in order to

- manage the trial in accordance with applicable regulations and internal SOPs,
- direct the clinical trial team in the preparation, conduct, and reporting of the trial,
- ensure appropriate training and information of Clinical Trial Managers (CT Managers), Clinical Research Associates (CRAs), and investigators of participating countries.

The organisation of the trial in China will be performed by the local or regional BI-organisation (Operating Unit, OPU) in accordance with applicable regulations and BI SOPs, or by a Contract Research Organisation (CRO) with which the responsibilities and tasks will have been agreed and a written contract filed before initiation of the clinical trial.

Data Management and Statistical Evaluation will be done by BI according to BI SOPs.

Tasks and functions assigned in order to organise, manage, and evaluate the trial are defined according to BI SOPs. A list of responsible persons and relevant local information can be found in the ISF.

A central laboratory service and an IRT vendor will be used in this trial. Details will be provided in the IRT Manual and Central Laboratory Manual, available in the ISF.

## 10. APPENDICES

### 10.1 BLOOD PRESSURE MEASUREMENT PROCEDURE

The preferred method for blood pressure measurement is electronic sphygmomanometer. If, for some reason, the electronic sphygmomanometer cannot be used for the measurement of blood pressure, a standard mercury sphygmomanometer may be used as an alternate method. Initially, blood pressure should be taken 3 times in both arms. If the pressures differ by more than 10 mmHg (as in the presence of a subclavian steal syndrome), the arm with the higher pressure (systolic or – if needed to decide- diastolic) should be used for subsequent measurements.

Blood pressure measurements should be performed on the same arm and, if possible, by the same person. The same method must be used throughout the trial, for a given patient, i.e., if a patient receives the first blood pressure measurement for example with an electronic device, the same method and the same model of device should be used throughout the study for this patient (without switching to manual blood pressure measurement). On the other hand, inter-patients variability is acceptable, i.e., a study site is allowed to consistently use an electronic device to measure the blood pressure in a given patient throughout the study and a manual technique in another patient.

After patients have rested quietly, in the seated position for five minutes, three blood pressure measurements will be taken approximately two minutes apart. The seated pulse rate of the second measurement will be used as the study data when an electronic device is used for the blood pressure measurement. In case of the measurement by using standard mercury sphygmomanometer, the seated pulse rate will be taken during the two-minute interval between the second and third blood pressure reading.

### 10.2 POTENTIAL MODIFICATION OF TRIAL CONDUCT IN CASE OF RESTRICTIONS DUE TO COVID-19

As mentioned in [section 6.1](#), in case of any restrictions during the COVID-19 pandemic, study conduct may need to be adjusted. The following contingency measures have been introduced to ensure patient safety and appropriate trial continuation based on a thorough benefit risk assessment (see Protocol [Section 1.4.2](#)).

In exceptional cases, when it is impossible to conduct the visits at the trial site, visits may be performed remotely (via telephone and/or internet based means of communication). Based on a thorough benefit-risk assessment (see Protocol Section 1.4.2), the visit procedures may be adjusted for the purpose of particular visits, whereby critical safety measures will remain in place. All remote visits need to be discussed with and approved by the sponsor's trial team. Local regulatory and legal requirements of the participating country need to be respected for all modifications.

Under these circumstances, the below modifications can be considered. Patients need to be informed about the modifications and agree to them before implementation:

Remote visit

If a patient is not able to come to the site for an outpatient visit, a remote visit (by phone) should be performed instead and all assessments that can be done by phone performed.

Assessments that should be performed during a remote visit are:  
Adverse Events, concomitant therapy, Diet and exercise counselling,

Safety lab, other laboratory tests

If taking blood samples for central lab is not possible, blood analysis for safety lab can be done in a local lab for remote visit 6. The results of the lab tests are to be reported and transferred to the investigator, who has to ensure medical review and proper documentation. Minimum required safety lab parameters are eGFR, liver enzymes and urine pregnancy test in women of child bearing potential which will be captured in the eCRF. A urine analysis should not be performed locally. On top of this the home blood glucose monitoring by the patient needs to be reported to the investigator at each remote visit 4, 5, 6 and 7 anyway.

COVID-19 PCR testing at remote visits is not part of trial procedures and may only be performed based on investigator judgement about the needs.

Dispensation of Trial medication (IMP)

If a patient is not able to come to visit 4, 5, 6 or 7 as planned but the investigator considers it favourable and safe for patient to continue with IMP, IMP can be shipped from site directly to the patient (if legally acceptable according to the local regulations). Temperature monitoring will be considered, and the documentation should be filed in ISF

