## FLOW CHART

Trial Periods	Screening	Run-in	Randomised Treatment					Follow-up
Visit	1	2	3	4 N	5 N	6 N	7 N	8 (EoT A )
Weeks	-3	-2	0	4	8	12	18	24
Study Day	-21	-14	1	29	57	85	127	169
Time window for visits	±7 days	-7 days	0	±7 days	±7 days	±7 days	±7 days	+ 7 days
Informed consent	X							
Demographics B	X	X						
Medical history	X							
In-/Exclusion criteria	X	X	X					
Physical examination		X						X
Vital signs	X	X	X	X	X	X	X	X M
Height	X							
HbA 1c	X		X	X	X	X	X	
Home Blood Glucose Monitoring C		X	X	X	X	X	X	X
Dispense placebo run-in kit D		X						
Randomisation (via IRT)			X					
Weight	X		X	X	X	X	X	
Waist circumference			X					X
Diet and exercise counselling E		X	X	X	X	X	X	
12 lead-ECG F			X					X
8-point glucose profile L			X			X		X
Pregnancy test G	X		X		X			X
Glomerular filtration rate H	X		X		X			X
Fasting C-peptide	X							
Safety lab tests I (urine and blood)	X I	X	X			X		X M
FPG		X	X	X	X	X	X	X M
2-hour PPG test J			X					X
Lipid lab panel			X					X
MTT test (including Insulin + c-peptide) J			X					X
Dispense trial drugs D			X	X	X	X	X	
All AEs/SAEs/AESIs K	X	X	X	X	X	X	X	X
Concomitant therapy	X	X	X	X	X	X	X	X
Compliance check			X	X	X	X	X	
Completion of patient participation								X

- A Patients who discontinue trial treatment prematurely should undergo the End of Treatment (EOT) visit as soon as possible and allow to attend all clinic visits up to the FUP Visit thereafter in order to collect all the data as other treatment completed patients.
- B Only screening relevant demographics (gender, date of birth, race and ethnicity) at Visit 1. Smoking and alcohol status could be collected at Visit 2.
- C Instruction and training of the patient to use the device at Visit 2. A full overnight fast (nothing to eat or drink except water for at least 10 hours) for all planned tests. Daily measurements during Run-in and Follow-up. During the treatment period a weekly test is recommended. During the whole trial participation, additional measurements should be done in case of hypo- or hyperglycemia related symptoms without fasting state required.
- D At all visits, the respective kit number has to be allocated to the patient via IRT.

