## 5.2.3 Safety laboratory parameters

Safety laboratory parameters to be assessed are listed in [Table 5.2.3: 1](#), [Table 5.2.3: 2](#) and [Table 5.2.3: 3](#). For the sampling time points please see the Flow Chart.

All analyses will be performed by a central laboratory, the respective reference ranges will be provided in the ISF.

Safety laboratory samples (C-peptide at Visit 1 and all other visits) will be collected after a full overnight fast (nothing to eat or drink except water for at least 10 hours) and before background antidiabetic therapies and investigational drug as described in the Flow Chart and [Section 6](#). The blood sample at Visit 1 (screening visit) except C-peptide can be taken with the patient in a fasted or nonfasted state.

Instructions regarding sample collection, sample handling/ processing and sample shipping are provided in the Laboratory Manual in the ISF.

The central laboratory will send reports to the investigator. It is the responsibility of the investigator to evaluate the laboratory reports. Clinically relevant abnormal findings as judged by the investigator will be reported as adverse events (please refer to [Section 5.2.6](#)).

In case the criteria for hepatic injury are fulfilled, a number of additional measures will be performed (please see [Section 5.2.6.1](#) and the DILI Checklist provided in the ISF and EDC system). The amount of blood taken from the patient concerned will be increased due to this additional sampling.

Reduced safety lab panels excluding urinalysis are planned for the following visits:

- For the screening Visit 1, laboratory only includes liver transaminases, alkaline phosphatase, serum creatinine and fasting C-peptide.
- Lipid fractions will only be determined at baseline (Visit 3) and end of treatment/ Visit 8

The central laboratory will transfer the results of the analysis to the sponsor.

Table 5.2.3: 1

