**Safety laboratory parameters – Clinical Chemistry**

• Amylase

• Lipase

• AST (aspartate transaminase,SGOT)

• ALT (alanine transaminase,SGPT)

• <math>\gamma</math>-GT (gamma-glutamyltransferase)

• Alkaline phosphatase

• Lactic dehydrogenase (LDH)

• Total bilirubin

• Direct bilirubin, if total bilirubin is elevated

• Total Protein

• Albumin

• C-peptide (at Visit 1 only)

• Creatine kinase (CK)/Troponin, if CK is elevated

	

• Potassium

• Sodium

• Bicarbonate

• Creatinine

• BUN

• Calcium

• Inorganic phosphorous

• Uric acid

• Cholesterol (total)*

• HDL cholesterol*

• LDL cholesterol*

• Triglycerides*

• Glucose

---	---

\*Visits 3, 8, EOT only

Table 5.2.3: 3

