##### Hepatic injury

A hepatic injury is defined by the following alterations of hepatic laboratory parameters:

- an elevation of AST (Aspartate Aminotransferase) and/or ALT (Alanine Aminotransferase)  $\geq 3$  fold ULN combined with an elevation of total bilirubin  $\geq 2$  fold ULN measured in the same blood draw sample, or
- Aminotransferase (ALT, and/or AST) elevations  $\geq 5$  fold ULN.

These lab findings constitute a hepatic injury alert and the patients showing these lab abnormalities need to be followed up according to the “DILI checklist” provided in the ISF and EDC system.

In case of clinical symptoms of hepatic injury (icterus, unexplained encephalopathy, unexplained coagulopathy, right upper quadrant abdominal pain, etc.) without lab results (ALT, AST, total bilirubin) available, the investigator should make sure these parameters are analysed, if necessary in an unscheduled blood test. Should the results meet the criteria of hepatic injury alert, the procedures described in the DILI checklist should be followed.

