If it is not recommended to conduct Visit 4, 5, 6 or 7 at the trial site, it may be performed remotely (via telephone and/or internet- based means of communication). In the event of a remote Visit 4, 5, 6 or 7 trial medication may be shipped by courier from site to patient, if legally acceptable according to local regulations and considered safe for patient to continue treatment. It is important that any remote Visit 4, 5, 6 and 7 is discussed with and approved by the sponsor/CRO to ensure delivery of trial medication fulfil the trial specific and country-specific requirements. All efforts should be made to at least perform two of the four visits with the patient visiting the site. The maximum time interval without a face to face contact with the patient should not exceed 16 weeks (e.g. the 12 week site visit could only be done remote if a face to face contact was performed at the 4 week or 8 week visit). The patient must be made aware of any conduct modifications and agreement needs to be obtained prior to them being implemented. See [Appendix 10.2](#) on the details of potential modification of trial conduct in case of restrictions due to COVID-19.

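### The minimum local safety panel for a remote Visit 6 leaves out total bilirubin, so one of the two hepatic-injury routes cannot be evaluated for an asymptomatic patient with ALT/AST at 3 to <5x ULN

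*Protocol*

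**What the plan says.** Protocol Section 10.2 covers visits that COVID-19 restrictions keep off site. If central samples cannot be taken, "blood analysis for safety lab can be done in a local lab for remote visit 6". The floor for that local testing is: "Minimum required safety lab parameters are eGFR, liver enzymes and urine pregnancy test in women of child bearing potential". The results go to the investigator for medical review, and the minimum parameters are entered in the eCRF.

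Protocol Section 5.2.6.1.4 gives two laboratory routes to hepatic injury:

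- AST and/or ALT at or above 3x ULN together with total bilirubin at or above 2x ULN, the latter "fold ULN measured in the same blood draw sample".
- ALT and/or AST at or above 5x ULN, with no bilirubin condition.

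The same section has a back-up for missing values, but clinical symptoms trigger it. For a symptomatic patient "without lab results (ALT, AST, total bilirubin) available, the investigator should make sure these parameters are analysed".

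The normal chemistry panel (Section 5.2.3, Table 5.2.3: 2) lists total bilirubin as an analyte of its own, followed by "Direct bilirubin, if total bilirubin is elevated".

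**The concern.** A minimum panel should secure the measurements that the safety definitions need, without relying on a site to do more than it is told. Here the floor drops one input to the definition of an adverse event of special interest. A site can follow Section 10.2 exactly and still be unable to say whether a patient with ALT or AST at 3 to <5x ULN meets the combined criterion.

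At stake is timeliness. Section 1.4.2 names drug-induced liver injury as a rare but severe risk to be managed by timely detection. Events of special interest are due to the sponsor within 24 hours (Sections 5.2.6.1.4 and 5.2.6.2.2). Meanwhile Section 10.2 lets trial medication be shipped to the patient if the investigator considers continuation safe. A combined transaminase and bilirubin signal in a patient without symptoms could go unrecognised at that visit.

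**Working it through.** The plan gives no figure to reproduce. The check sets what each route needs against what the floor supplies.

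**1. Does the floor include bilirubin?** It asks for liver enzymes. Bilirubin is not an enzyme, and Section 5.2.6.1.4 and Table 5.2.3: 2 both name it separately from ALT and AST. The Visit 1 panel in Section 5.2.3 (transaminases, alkaline phosphatase, creatinine, C-peptide) shows that a reduced liver panel in this protocol can omit it.

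**2. Which patients can be classified on the floor alone?**

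| ALT/AST | Input needed | On the floor? | Classifiable? |
|---|---|---|---|
| <3x ULN | enzymes | yes | yes, neither route met |
| 3 to <5x ULN | enzymes and same-draw bilirubin | bilirubin missing | no |
| >=5x ULN | enzymes | yes | yes, second route met |

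**3. Does another rule require the missing value?**

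- The back-up in Section 5.2.6.1.4 needs clinical symptoms, so it does not reach an asymptomatic patient.
- The DILI checklist follows once a criterion is met. In the middle row, that is what cannot be determined.
- Sections 5.2.3 and 5.2.6.2.2 lead to adverse-event reporting and follow-up if the investigator judges the result clinically relevant. They do not name bilirubin.
- Section 6.1 asks for on-site contact ("All efforts should be made to at least perform two of the four visits with the patient visiting the site"), but the flow chart row "Safety lab tests" shows no mark at Visits 4, 5 or 7.

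**4. When is the next scheduled bilirubin?** Flow chart study days: Visit 6 = 85 (±7), Visit 8 = 169 (+7).

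- Nominal gap: 169 − 85 = 84 days.
- Shortest: 169 − 92 = 77 days. Longest: 176 − 78 = 98 days.
- If the Visit 8 window were ±7 days, the shortest would be 162 − 92 = 70 days.

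These are approximate, because cells are displaced in the text copy of the flow chart. The HbA1c row has no mark at Visit 8, although Section 5.1 samples HbA1c at every visit except Visit 2. The last mark in the safety-laboratory row carries the footnote for adverse events persisting at Visit 8, which fits the follow-up visit better. Two points have support elsewhere: Section 10.2 treats Visit 6 as a safety-laboratory visit, and Section 5.2.3 has chemistry at Visit 8. The absence of a safety laboratory at Visits 4, 5 and 7 rests on the damaged row alone. In any case a later sample is not the same draw.

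**The case against.** The best case against the point is that it is remote and partly covered.

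- Section 10.2 sets a floor, and a site may run the full panel.
- The gap needs a sponsor-approved remote Visit 6, no central sampling, a site doing only the minimum, ALT/AST at 3 to <5x ULN, no symptoms (jaundice would count as one) and no discretionary retest. For an event to be missed, bilirubin must also be at or above 2x ULN.
- Exclusion criterion 13 removes patients above 3x ULN at Visit 1.
- A relevant enzyme rise can be reported as an adverse event, which must then be followed up.
- Section 3.1 provides blinded external review of certain hepatic events and mentions liver enzyme elevations. An enzyme-only rise may therefore qualify, but the charter is not in the documents.
- SAP Section 7.8.1.5 also summarises hepatic adverse events by standardised queries, which need no bilirubin value.

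All of this stands and limits the size of the point. None of it requires a bilirubin for the asymptomatic patient.

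Three stronger readings are tempting, and the documents do not support them.

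- *Without the local ULNs, neither criterion can be applied.* Section 10.2 does not ask for them, and for the central laboratory Section 5.2.3 says "the respective reference ranges will be provided in the ISF". But local reports are kept as source (Section 8.3.1) and may show the local range, and the eCRF pages are not available to check. A range can probably be recovered; a bilirubin never measured cannot.
- *The SAP loses these patients.* SAP Section 7.8.2.1 first counts every patient with AST/ALT at or above 3x, 5x, 10x and 20x ULN, with no bilirubin condition. Only the bilirubin-conditional displays leave out patients whose bilirubin is unknown, and that is correct classification.
- *Hepatic injury goes undetected altogether under the contingency.* The 5x route needs enzymes only.

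**Conclusion.** The point holds, as a minor one. On the Section 10.2 minimum, one of the two laboratory routes for one of the four adverse events of special interest cannot be evaluated for an asymptomatic patient at 3 to <5x ULN. The number of patients affected is unknown, because the documents give no rate of remote Visit 6.

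The conclusion assumes that a site does no more than the minimum and that liver enzymes is read in its ordinary sense. It does not depend on the exact interval to the next scheduled bilirubin. The primary HbA1c analysis and the sample size are unaffected.

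**What to change.** In Protocol Section 10.2:

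- Add total bilirubin, from the same draw as ALT and AST, to the minimum local panel for a remote Visit 6.
- Add one sentence: if ALT or AST is at or above 3x ULN and no bilirubin was run, ALT, AST and total bilirubin are repeated together in a single unscheduled draw as soon as possible.

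Optionally, record the local ULNs for these three analytes in the eCRF. This is a minor aid.

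The cost is one more analyte on blood already being taken, a matching eCRF field, and an occasional repeat draw. The SAP needs no change.
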